### **4.3.3 Women of Childbearing Potential**

A Women of childbearing potential (WOCBP) is defined as any female who has experienced menarche and who has not undergone surgical sterilization (hysterectomy or bilateral oophorectomy) and is not postmenopausal. Menopause is defined as 12 months of amenorrhea in a woman over age 45 years in the absence of other biological or physiological causes. In addition, females under the age of 55 years must have a serum follicle stimulating hormone, (FSH) level > 40mIU/mL to confirm menopause.

\*Females treated with hormone replacement therapy, (HRT) are likely to have artificially suppressed FSH levels and may require a washout period in order to obtain a physiologic FSH level. The duration of the washout period is a function of the type of HRT used. The duration of the washout period below are suggested guidelines and the investigators should use their judgement in checking serum FSH levels. If the serum FSH level is >40 mIU/ml at any time during the washout period, the woman can be considered postmenopausal :

- 1 week minimum for vaginal hormonal products (rings, creams, gels)
- 4 week minimum for transdermal products
- 8 week minimum for oral products

Other parenteral products may require washout periods as long as 6 months.

## **5 STUDY DESIGN AND INTERVENTION**

### **5.1 Screening Visit**

Potential subjects will be screened using the protocol inclusion and exclusion criteria. All subjects will have a diagnosis of AF with TIA or small to medium ischemic stroke.

Subject consent will be obtained prior to any study related procedures being performed. All females of child bearing age will have a urine pregnancy test within 24 hours of starting study drug. Labs to assess liver and kidney function and an EKG will be obtained from the patients' hospital record or obtained at screening. A physical exam will be obtained at screening. The screening and baseline/randomization may be combined as long as all inclusion/exclusion criteria have been met prior to randomization. Otherwise, if these reports are not available at the time of screening, patients

will be required to return for a separate assessment visit after these items are obtained. Drug initiation visit may take place in hospital or as a clinic visit.

**5.2 Baseline Visit/Randomization**

The baseline/randomization visit will be performed up to 48 hours after signs and symptoms of stroke or TIA, and will be combined with the screening visit as long as all inclusion/exclusion criteria have met prior to randomization.

After subjects have been screened and enrolled in the study, baseline assessments will be performed. Patients will be stratified according to their type of stroke ( TIA, small or medium stroke) and randomized 1:1 in each group to ensure for equal number of subjects for each three types. Treatment with APIXABAN 5mg or 2.5mg based on clinical characteristics defined in section 1.4 or Warfarin ( target INR 2-3) will begin based on the randomization treatment regimen. Study treatment regimen is initiated based off of TIA or stroke size. Subjects in the Warfarin arm will return to clinic with unscheduled INR checks until they reached the standard INR of 2.0 to 3.0.

Hypertension will be treated per the AHA/ASA guidelines and are described below:

Goals for target blood pressure level or reduction from pretreatment baseline are uncertain and should be individualized, but it is reasonable to achieve a systolic pressure less than 140 mm Hg and a diastolic pressure less than 90 mm Hg. For patients with a recent lacunar stroke, it might be reasonable to target a systolic blood pressure of less than 130 mm Hg.

Resumption of Blood Pressure therapy is indicated for previously treated patients with hypertension.

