## Schedule of Study Procedures

TIA -Apixaban group	Screen/ Baseline	Treatment Initiation	Maintenance ‡						End of Study	30day PC	Early Withdrawal	Unsch
			3	4	5	6	7	8				
Visit Number	1	2	3	4	5	6	7	8	9	10		
Study Days (Visit Window)	0	$\beta$ (See also table 2)	14 ( $\pm 3$ )	30 ( $\pm 5$ )	60 ( $\pm 10$ ) )	90 ( $\pm 10$ ) )	120 ( $\pm 10$ ) )	150 ( $\pm 10$ ) )	180 ( $\pm 10$ )	210 ( $\pm 10$ ) )		
Informed Consent	✓											
Inclusion/Exclusion Criteria	✓											
General Medical History/Demographics	✓											
Physical Exam	✓		✓	✓	✓	✓	✓	✓	✓		✓	✓
Vital Signs §	✓		✓	✓	✓	✓	✓	✓	✓		✓	✓
mRS	✓		✓	✓	✓	✓	✓	✓	✓		✓	
NIHSS	✓		✓	✓	✓	✓	✓	✓	✓		✓	✓
SS-QOL	✓			✓					✓		✓	✓
Urine pregnancy test †	✓	✓ †	✓	✓	✓	✓	✓	✓	✓		✓	
12-lead ECG	✓		✓	✓	✓	✓	✓	✓	✓		✓	✓
Clinical Lab Evaluation*	✓ **			✓		✓			✓		✓	✓
PT/INR ( Warfarin arm only)		✓	✓	✓	✓	✓	✓	✓	✓		✓	✓
TEE	✓ †											
Event Monitor (prior to DC)		✓										
Carotid Ultrasound	✓											
MRI or CT scan	✓		✓						✓		✓	
Record AE/SAEs		✓	✓	✓	✓	✓	✓	✓	✓	✓	✓	✓
Prior and con. medications/procedures	✓	✓	✓	✓	✓	✓	✓	✓	✓	✓	✓	
Dispense Study Drug		✓	✓	✓	✓	✓	✓	✓				✓
Drug Compliance			✓	✓	✓	✓	✓	✓	✓		✓	✓
Non-study anticoagulation initiation									✓		✓	

$\beta$  drug initiation will be as follows: TIA: Apixaban arm day 0-3/Warfarin arm day 7( $\pm 5$ ): Small stroke: Apixaban arm day 3-5/Warfarin arm day 14( $\pm 5$ ): Medium stroke: Apixaban arm day 7-9/Warfarin arm day 14( $\pm 5$ )

\* Results of existing tests will be obtained from subject's hospital chart to assess eligibility. If tests results are not available labs will be performed at the visit. See section 6 for a detailed description of what this entails.

§ Vitals: BP, HR,, weight, (RR and Temperature are optional, height obtained at baseline only)

\*\* Labs for inclusion/exclusion criteria will include CMP, CBC with diff and platelets, Creatinine, PT/INR, LFTs and Lipid panel.

† performed prior to discharge

† All WOCBP MUST have a negative pregnancy test within 24 hours before receiving apixaban. The minimum sensitivity of the pregnancy test must be 25 IU/L or equivalent units of HCG. If the pregnancy test is positive, the subject must not receive apixaban and must not be enrolled in the study. † Study day at screening is day of event

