## 5.6 Unscheduled Visits

### 5.6.1 Super-therapeutic/Sub-therapeutic INR

If the subject is not within therapeutic range they will be expected to return to clinic for an unscheduled visit to check the INR value until therapeutic range is met per the warfarin dosing protocol. These visits will be scheduled per PI discretion.

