### 5.6.2 Adverse Events

If the subject reports an adverse event that requires medical investigation an unscheduled visit will be arranged. This can be arranged through the site coordinator. All medically relevant diagnostic tests will be performed at that time.

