## 7.5 Efficacy and Safety Evaluations (see also schedule of events)

### 7.5.1 Diagnostic Tests, Scales, Measures, etc.

*MRI w/o contrast (GRE sequencing preferred but all effort should be used to maintain the same modality of sequencing and magnet strength from baseline or CT w/o contrast –*

Will be performed, along with the NIHSS, to measure the size of ischemic stroke at screening. It will also be used for follow-up assessments to indicate any early hemorrhagic transformation or micro-embolic strokes. Patients who are unable to have a MRI due to contraindication (i.e. implantable pacemaker) will have be allowed to use CT with the NIHSS.

- TIA- will have no ischemic changes
- Acute infarcts are classified as small, medium or large based on size of the largest ischemic lesion:
  - small = lesion in the anterior or posterior circulation <1.5 cm.
  - medium = equal to or greater than 1.5cm but less than a complete territory infarct lesion in a cortical superficial branch of the anterior cerebral artery (ACA), middle cerebral artery (MCA), posterior cerebral artery (PCA), or in a branch of MCA or PCA, or lesion in internal border-zone territories.
  - large posterior = lesion involving complete PCA territory, or lesion of cerebellum 1.5 cm or larger or any lesion of the brain stem.
  - large anterior = lesion involving complete ACA or MCA territory, or lesion involving >1 artery territory
- All classifications are based of the measurement of the largest lesion size.

*TEE-*

Will be obtained or scheduled prior to discharge on all patients or will be scheduled as part of their evaluation for potential cardiac sources of emboli. In addition to imaging specifically of left atrium thrombus; measurements will be obtained for left atrial size, left atrium appendage, velocity, left ventricle size and function and other significant myocardial or valvular heart disease.

*Carotid ultrasound-*

Will be performed on all patients to rule out ipsilateral carotid disease during the screening visit.

*Laboratory evaluations-*

Will be obtained from all patients at screening, day 30, day 90 and day 180. Additional lab measurements for the warfarin group will be obtained monthly and at unscheduled visits if warranted by the warfarin dosing protocol.

*Event Monitor-*

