### 10.3 Definition of an Adverse Event

#### An Adverse Event

[AE] is defined as any new untoward medical occurrence or worsening of a pre existing medical condition in a patient or clinical investigation subject administered an investigational (medicinal) product and that does not necessarily have a causal relationship with this treatment. An AE can therefore be any unfavorable and unintended sign (including an abnormal laboratory finding, for example), symptom, or disease temporally associated with the use of investigational product, whether or not considered related to the investigational product.

- The causal relationship to study drug is determined by a physician and should be used to assess
- all adverse events (AEs). The causal relationship can be one of the following:
  - **Related:** There is a reasonable causal relationship between study drug administration and the AE.
  - **Not Related:** There is not a reasonable causal relationship between study drug administration and the AE.
- The term “reasonable causal relationship” means there is evidence to suggest a causal relationship.
- Adverse events can be spontaneously reported or elicited during open-ended questioning, examination, or evaluation of a subject. (In order to prevent reporting bias, subjects should not be questioned regarding the specific occurrence of one or more adverse events).

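### INR-only return visits occur in the warfarin arm alone, and the undivided unscheduled-visit column attaches NIHSS, examination, ECG and AE recording to them, so mild clinical events get more chances of detection on warfarin

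*Combined protocol and SAP*

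**What the plan says.** All references are to the combined protocol and SAP.

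- **Start of warfarin (5.2):** "Subjects in the Warfarin arm will return to clinic with unscheduled INR checks until they reached the standard INR of 2.0 to 3.0". The number of visits is not stated.
- **Later in treatment (5.6.1):** for an INR out of range, "they will be expected to return to clinic for an unscheduled visit to check the INR value", repeated until the range is met, with timing at the investigator's discretion.
- **Laboratory contacts (7.5.1):** "Additional lab measurements for the warfarin group will be obtained monthly and at unscheduled visits if warranted by the warfarin dosing protocol".
- **Schedule of Study Procedures:** the INR row is labelled "PT/INR ( Warfarin arm only". The single unscheduled-visit column ticks physical examination, vital signs, NIHSS, SS-QOL, ECG, laboratory tests, INR, dispensing, compliance and "Record AE/SAEs". It does not tick mRS or MRI/CT. It does not separate INR visits from adverse event visits.
- **Unscheduled visits open to both arms (5.6.2):** "If the subject reports an adverse event that requires medical investigation an unscheduled visit will be arranged".
- **NIHSS and SS-QOL timing in the text:** 5.5 and 7.5.1 place the NIHSS at screening and days 14, 30, 60, 90, 120, 150 and 180; 7.5.1 adds early withdrawal. Section 5.5 places SS-QOL at screening, day 30 and end of study or early withdrawal. Neither section names unscheduled visits for these scales.
- **AE enquiry (10.3):** "subjects should not be questioned regarding the specific occurrence of one or more adverse events", although open-ended questioning and examination are allowed.

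**The concern.** The trial is open label (4.1) and the stroke adjudicators know the treatment arm (2.3). If one arm is seen and examined more often, events that do not force a patient to seek care are more likely to be recorded there. TIA is the clearest case. By the definition in 2.3.2 the symptoms resolve and imaging shows no acute damage, so neither a later NIHSS nor the day 14 or day 180 scan need show it. Mild recurrent stroke and minor AEs share the problem to a lesser degree.

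The extra contacts fall in the control arm, so for these events the bias favours apixaban. Section 8 has no analysis for unequal ascertainment, and no rule ties endpoint ascertainment to the visits that both arms share. Warfarin starts around day 7 or day 14, so first titration falls largely before the day 30 reading of the primary outcome. Section 8.1.5 says the data are meant to inform larger studies, so a detection artefact could carry into their planning.

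**Working it through.** The plan gives no figure to reproduce. The check is a reading of the schedule against the text, followed by illustrations on stated assumptions.

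**1. Is the extra contact one-sided?** Yes. The visits in 5.2 and 5.6.1 depend on an INR, which the schedule measures after baseline in the warfarin arm only. Section 5.6.2 applies to both arms and needs a reported event. The schedule's title names the TIA apixaban group, but its warfarin-only row and its footnotes for both arms show that it serves both.

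**2. Do those visits carry event-finding procedures?** By the schedule, yes. By 5.6.1 the purpose is to check the INR, and 5.5 and 7.5.1 leave unscheduled visits out of the NIHSS timing. The places disagree, and sites could follow either.

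**3. How many more examinations?** Each arm has 7 scheduled post-baseline NIHSS examinations. The number k of INR visits per warfarin patient is an assumption; the ratio is (7 + k)/7.

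| k | Warfarin vs apixaban | Ratio |
|---|---|---|
| 1 | 8 vs 7 | 1.14 |
| 2 | 9 vs 7 | 1.29 |
| 4 | 11 vs 7 | 1.57 |
| 6 | 13 vs 7 | 1.86 |

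**4. Illustration for contact-dependent events.** Assume 8 scheduled contacts per arm (visits 2 to 9), k = 4 to 8 extra on warfarin, half of all contacts falling after the event, and a chance q = 0.10 to 0.20 per contact that the event comes to light. Detection = 1 − (1 − q)^m, with m = 4 on apixaban and m = 4 + k/2 on warfarin.

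| q | k | Apixaban | Warfarin | Ratio seen if the true ratio is 1.0 |
|---|---|---|---|---|
| 0.10 | 4 | 1 − 0.9^4 = 0.344 | 1 − 0.9^6 = 0.469 | 0.73 |
| 0.10 | 8 | 0.344 | 1 − 0.9^8 = 0.570 | 0.60 |
| 0.20 | 4 | 1 − 0.8^4 = 0.590 | 1 − 0.8^6 = 0.738 | 0.80 |
| 0.20 | 8 | 0.590 | 1 − 0.8^8 = 0.832 | 0.71 |

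Warfarin initiation after stroke (day 14 ± 5) can coincide with visit 3 (day 14 ± 3); apixaban initiation after stroke (days 3–5 or 7–9) cannot. Taking one scheduled contact from warfarin (m = 3.5 + k/2) moves the range to 0.63–0.84.

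**5. Dilution in the composite.** Section 1.2 reports 24.7% mortality before discharge and 5.1% non-fatal recurrence in survivors. Assume that this mix held, that only the non-fatal recurrences depend on contact, and that TIA is not counted. The contact-dependent share is 0.753 × 0.051 / (0.247 + 0.753 × 0.051) = 0.0384 / 0.2854 = 13.5%. The composite ratio is then 0.865 + 0.135 × 0.60 = 0.95 to 0.865 + 0.135 × 0.80 = 0.97. If TIA counts and half of all events are contact-dependent (an assumption), it is 0.5 + 0.5 × 0.60 = 0.80 to 0.5 + 0.5 × 0.80 = 0.90.

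**6. Chance of a false positive for apixaban.** Assume a true risk of 20% in both arms (the control risk in 8.1.5), 60 per arm, full detection on warfarin and a two-sided 5% test with pooled variance.

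| Composite ratio seen | Observed risks | Chance of a significant result favouring apixaban (nominal 2.5%) |
|---|---|---|
| 0.95 | 20% vs 19% | 3.4% |
| 0.90 | 20% vs 18% | 4.6% |
| 0.80 | 20% vs 16% | 8.2% |

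**The case against.** INR monitoring is inherent to an open-label warfarin comparator, and this is a pilot. The unscheduled column may have been meant for adverse event visits: 5.6.1 speaks only of the INR, and SS-QOL at every INR check would go beyond the timings in 5.5. This stands as a reason to call the documents ambiguous. It does not remove the point, because the column as printed makes no such distinction.

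Four stronger readings are tempting and are not supported.

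- **That a transient event is found only if the patient volunteers it.** Section 10.3 allows open-ended elicitation, examination and evaluation, and both arms have examination, NIHSS and mRS at seven common visits.
- **That 0.60–0.80 is the bias in the primary result.** Every input is assumed. The model gives no credit to scheduled examination or to MRI/CT, treats mild stroke like TIA, and spreads evenly visits that 5.2 places around warfarin start.
- **That safety is biased throughout.** MRI/CT is taken at day 14 and end of study in both arms and is absent from the unscheduled column. Major bleeding in 7.2 needs overt bleeding that meets set criteria. Section 10.5.4 starts non-serious AE collection at drug initiation, generally earlier on apixaban, which partly offsets the AE imbalance.
- **That the bias could never be examined later.** Section 2.2 has data recorded as they are collected at visits, so some reconstruction may be possible. But the plan does not call for recording which contact first brought an event to light.

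**Conclusion.** The point holds in a limited form. The extra INR visits are warfarin-only, and the undivided column attaches event-finding procedures to them. The schedule and sections 5.5, 5.6.1 and 7.5.1 must be reconciled. If the schedule is followed, clinically detected mild recurrent stroke, TIA and minor AEs get more chances of detection on warfarin, which favours apixaban. TIA is a primary component in 3.2 and 8.1.2 but not in 7.1, so its weight depends on which definition governs.

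The direction for these events follows from the visit structure; the size does not. INR visit frequency is not given. The 0.60–0.80 range applies to contact-dependent events only, and the composite would move less: 0.95–0.97 with the event mix of 1.2, or 0.80–0.90 if half of the events were contact-dependent. Fatal and disabling strokes and MRI/CT-assessed intracranial bleeding are largely unaffected. It is worth correcting because the correction is cheap.

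**What to change.** 1. **Split the unscheduled column.** An INR-only visit carries no routine NIHSS, SS-QOL, ECG or physical examination. Any complaint volunteered there is still recorded and opens an adverse event visit under 5.6.2 with the full set. Align 5.5, 5.6.1 and 7.5.1 with the result. INR monitoring itself is untouched.
2. **Equalise the enquiry.** At scheduled visits 3 to 9 in both arms, ask the same scripted questions on stroke, TIA and bleeding symptoms, with a stated exception to 10.3. This matters because step 1 alone leaves volunteered reports at INR visits one-sided.
3. **Record the source.** Add a CRF field for the contact at which each event was first reported. Keep the primary analysis unchanged. Add a sensitivity analysis of the primary and AE comparisons without events first reported at INR-only visits. Label it as a bound: it removes events from the warfarin arm only, including some that the next scheduled visit would have found, and may over-correct against apixaban.

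Cost: a schedule change, a short script, one CRF field, one added analysis and a little more site time at scheduled visits, set against fewer procedures at INR visits.

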**5.3 Treatment Phase**

A study visit for the initiation of treatment will be conducted based on dosing category of TIA, Small stroke or medium stroke. See table 2 below and figure 1:

Dosing Category	Apixaban dose initiation window
TIA	Day 0-3
Small Stroke	Day 3-5
Medium Stroke	Day 7-9
Dosing Category	Warfarin dose initiation window
TIA	Day 7 (+/-5)
Small Stroke	Day 14 (+/-5)
Medium Stroke	Day 14( +/-5)

Table 2

Subjects will maintain the maximum dose for approximately 180 days (depending on dosing category) with study visits at drug initiation, day 14, 30, 60, 90, 120, 150 and 180. Patients will undergo drug accountability, AE/SAE assessment, and any concomitant medication changes.

## 5.4 End of Study

A final visit will be conducted at day 180 in person. Study medication will be collected at this visit and the patient will be started on standard of care therapy. Decisions regarding anticoagulation will be based off the subject's individual needs as assessed by the Principal Investigator or Sub-Investigator.

30 days after the EOS a phone call will be made to assess for AE's or SAE's that may have occurred during that time frame.

## 5.5 Study Assessments (See figure 1)

The NIHSS and mRS Stroke will be obtained at screening and days 14, 30, 60, 90, 120, 150 and 180. MRI (or CT for subjects with contraindication to MRI) will be obtained at day 14 and EOS or Early Withdrawal (EW).

The Stroke Specific Quality of Life Scale (SS-QOL) will be conducted on screening day and again on day 30 and at EOS or EW.

## 5.6 Unscheduled Visits

### 5.6.1 Super-therapeutic/Sub-therapeutic INR

If the subject is not within therapeutic range they will be expected to return to clinic for an unscheduled visit to check the INR value until therapeutic range is met per the warfarin dosing protocol. These visits will be scheduled per PI discretion.

### 5.6.2 Adverse Events

If the subject reports an adverse event that requires medical investigation an unscheduled visit will be arranged. This can be arranged through the site coordinator. All medically relevant diagnostic tests will be performed at that time.

## 5.7 Subject Completion/Early Withdrawal

It will be documented whether or not each subject completed the clinical study. A subject is considered to have completed the study if he/she has taken all study medications for 6 months and has completed 6 month study assessments or withdrew from the study due to the occurrence of a recurrent embolic stroke, hemorrhagic transformation or death. If a subject does not complete the treatment phase, their data will be used for efficacy and for any safety analysis.

It is understood that withdrawals may occur during a trial. Each subject has the right to withdraw from the trial at any time for any reason without affecting the right to treatment by the investigator. Subjects who do not complete the treatment phase for other reasons then mentioned above, should be followed at day 14 and EOS visits, if possible. At minimum these patients should have a monthly phone call to assess AE/SAE and vital status if they are unable to continue follow-up in clinic.

Subjects needing to withdraw prior to the completion of the study and who do not agree to continue in follow-up should return to the clinic for completion of early withdrawal procedures, as outlined in table 1.

Reasons that a subject may discontinue the study include the following:

- Adverse events including recurrent stroke or hemorrhagic transformation
- Intercurrent illnesses
- Any significant new medical condition
- Protocol violation
- Non-compliance to study medication regimen

- Use of any investigational drug other than the study medication
- Intake of prohibited medication
- Pregnancy
- Subject withdrew consent or lost to follow-up
- Other (reason to be documented)

Withdrawals due to intercurrent illnesses or AEs will be fully documented in the CRF with the addition of supplementary information if available and/or appropriate. Withdrawals due to non-attendance will be followed-up by the investigator to obtain the reason for non-attendance.

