### **7 STUDY ENDPOINTS AND EVALUATIONS**

#### **7.1 Primary Endpoint**

Endpoint data will start at randomization up to 180 days. These composite endpoints include:

- Fatal stroke
- Recurrent Ischemic stroke
- New hemorrhagic stroke

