#### For individual patients

In the event of a Grade 3 or higher adverse event attributable to treatment with APIXABAN and not related to the underlying disease, administration of APIXABAN will be suspended in the patient to allow analysis and determination whether to continue the treatment, alter dosing regimen or to exclude the patient from further participation in the study; if there is any increase in cerebral microbleeds (CMB) at day 14, in either arm, all study medication will be suspended until a repeat MRI is performed 48 hours from day 14 MRI. Study medication will be restarted in clinically stable individuals. In subjects who have a CT scan at day 14 and have a asymptomatic intracranial hemorrhage, all study medication will be suspended until a repeat CT is performed at 48 hours from the day 14 scan. Sstudy medication will be restarted in clinically stable individuals. If subjects experience any symptomatic hemorrhagic transformation in either arm, study medication will be suspended. All subjects will continued to be followed up monthly either by phone or clinic contact until the end of study.

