#### **10.4.1 Serious Adverse Event Collecting and Reporting**

Following the subject’s written consent to participate in the study, all SAEs, whether related or not related to study drug, must be collected, including those thought to be associated with protocol-specified procedures. All SAEs must be collected that occur during the screening period and within 30 days of discontinuing dosing. If applicable, SAEs must be collected that relate to any later protocol-specific procedure (such as follow-up skin biopsy).

The investigator should report any SAE occurring after these time periods that is believed to be related to study drug or protocol-specified procedure.

An SAE report should be completed for any event where doubt exists regarding its status of seriousness.

If the investigator believes that an SAE is not related to study drug, but is potentially related to the conditions of the study (such as withdrawal of previous therapy, or a complication of a study procedure), the relationship should be specified in the narrative section of the SAE Report Form.

SAEs, whether related or unrelated to the study drug, and pregnancies must be reported to BMS within 24 hours. SAEs must be recorded on the SAE Report Form; Pregnancies on a Pregnancy Surveillance Form.

**SAE Email Address:** [contact]

**SAE [contact]

If only limited information is initially available, follow-up reports are required. (Note: Follow-up SAE reports should include the same investigator term(s) initially reported.)

If an ongoing SAE changes in its intensity or relationship to study drug or if new information becomes available, a follow-up SAE report should be sent within 24 hours to the BMS (or designee) using the same procedure used for transmitting the initial SAE report.

All SAEs should be followed to resolution or stabilization.

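### Section 5.7 counts patients who leave after a recurrent stroke or hemorrhagic transformation as completers and omits them from its follow-up duty, in conflict with Section 7.5.2, so follow-up may end at an outcome event

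*Combined protocol and SAP*

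**What the plan says.** Section 5.7 has two routes to completion: six months of medication and assessments, or having been a patient who "withdrew from the study due to the occurrence of a recurrent embolic stroke, hemorrhagic transformation or death". The follow-up rule then covers a different group: "Subjects who do not complete the treatment phase for other reasons then mentioned above, should be followed at day 14 and EOS visits, if possible". The monthly call is a fallback for that same group. Among the reasons for discontinuing the study, not just the drug, Section 5.7 lists "Adverse events including recurrent stroke or hemorrhagic transformation". It also says: "If a subject does not complete the treatment phase, their data will be used for efficacy and for any safety analysis".

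Section 7.5.2 (For individual patients) takes another line. "If subjects experience any symptomatic hemorrhagic transformation in either arm, study medication will be suspended", and the paragraph ends: "All subjects will continued to be followed up monthly either by phone or clinic contact until the end of study".

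On what has to be observed, Section 7.1 says: "Endpoint data will start at randomization up to 180 days". Section 7.2 has intracranial bleeds assessed by scan at day 14, at end of study (EOS) or at an outcome event. Section 8.1.3 codes intracranial hemorrhage 0 or 1 at 30 and 180 days. Section 8.1.4 promises sensitivity analyses for missing outcomes, but names only the primary result.

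**The concern.** Read alone, Section 5.7 gives a patient who stops for non-compliance a stated follow-up duty and a patient with a recurrent stroke none. Section 7.5.2 points the other way, so a site can follow either section and be within the protocol.

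What is at stake depends on the event.

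- **After a non-fatal recurrent ischemic stroke**, the composite is already met. What can still be lost is later intracranial hemorrhage (above all silent bleeds seen only on the EOS scan), later major bleeding, the fatal-stroke component, and day-180 mRS, NIHSS and SS-QOL. Section 3.1 hypothesises fewer such strokes on early apixaban, so this loss would differ by arm.
- **After hemorrhagic transformation**, the intracranial hemorrhage outcome is already 1. The composite in Section 8.1.2, however, consists of fatal stroke, recurrent ischemic stroke and TIA, without hemorrhagic stroke. Under that version a later primary event could be missed. Under Section 7.1, which lists new hemorrhagic stroke, the transformation would usually count as the event.

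The plan does not say how a patient who left after an event is coded for a later outcome. Someone labelled a completer could pass as hemorrhage-free without a day-180 scan.

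**Working it through.** **Reading the sections together.** The closing sentence of Section 7.5.2 ends a paragraph on suspending dosing for adverse events and bleeding. Narrowly read, it covers those patients. Literally read, it covers everyone, including patients with recurrent ischemic stroke. On either reading a phone contact meets it, and a phone contact cannot replace a scan.

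**Inputs.** The plan gives no figure for event-driven exits, so none can be reproduced.
- 60 patients per arm: 120 at 1:1 (Sections 4.2.2 and 11.1).
- Warfarin-arm event risk: 5.1% non-fatal recurrence in the local database review (Section 1.2, time horizon not stated), or 20% fatal or recurrent stroke (Section 8.1.5).
- Warfarin-to-apixaban risk ratio: 2.30, from the 80% row of the table in Section 8.1.5. It is borrowed only to set the size of the arm difference. With 20% as the control risk and 50 per group, power at that ratio is 36.2%, not 80%. That is a separate matter, and nothing below uses the power claim.
- Assumed: every patient with an event leaves on the event day, at a mean of day 30 (range 15 to 90).

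**Patients affected** = 60 × risk.
- 5.1%: 60 × 0.051 = 3.1 warfarin; 60 × 0.051/2.30 = 1.3 apixaban.
- 20%: 60 × 0.20 = 12 warfarin; 60 × 0.20/2.30 = 5.2 apixaban.

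**Share of planned follow-up lost** = patients × (180 − event day) / (60 × 180).

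| Warfarin risk | Mean day 15 | Mean day 30 | Mean day 90 |
|---|---|---|---|
| 5.1% | 4.7% vs 2.0% | 4.3% vs 1.8% | 2.6% vs 1.1% |
| 20% | 18.3% vs 8.0% | 16.7% vs 7.2% | 10.0% vs 4.3% |

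(Warfarin first.) All these figures shrink in proportion to the share of event patients who actually leave.

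**Effect on the hemorrhage comparison.** Suppose hemorrhage risk is equal in the arms and unrelated to recurrence, and a fraction f of hemorrhages in patients with recurrence is missed (assumed 0.5 to 1). Then observed risk ratio (apixaban/warfarin) = (1 − f × apixaban recurrence) / (1 − f × warfarin recurrence).
- 5.1% vs 2.2%: 0.9889/0.9745 = 1.015 (f = 0.5); 0.9778/0.949 = 1.030 (f = 1).
- 20% vs 8.7%: 0.9565/0.90 = 1.063 (f = 0.5); 0.913/0.80 = 1.141 (f = 1).

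The hemorrhage rate cancels from these ratios. At an assumed rate of 2 to 10%, the expected number missed on warfarin is 60 × recurrence × rate × f: 0.03 to 0.31 at 5.1%, and 0.12 to 1.20 at 20%. If hemorrhage were four times as likely after recurrence (assumed, 20% case), a true ratio of 0.79 would be seen as 0.91 to 1.14.

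**The case against.** The strongest reply is that little is lost. Exit is permitted, not required. Section 7.5.2 suspends the drug and keeps contact to the end of study. A scan at the outcome event catches hemorrhage present at the recurrence (Section 7.2). The early-withdrawal visit includes a scan, NIHSS, mRS and SS-QOL (Section 6.6). On serious events: "All SAEs must be collected that occur during the screening period and within 30 days of discontinuing dosing". Monthly contact can pick up deaths, symptomatic strokes and major bleeds. The 0/1 coding makes some later events irrelevant.

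Most of this stands, and it narrows the point. What it leaves open is the period after exit. An early-withdrawal scan is taken at exit. If dosing stopped at day 30, routine SAE collection would end at day 60, with 120 days of the endpoint window left. Using the data of those who stop early creates no new observations.

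A reader might infer that everyone with an event is lost, so that 12 warfarin and 5 apixaban patients would be truncated. The documents do not support that: no exit rate is given, Section 7.5.2 says otherwise, and the 20% includes fatal strokes, after which there is no follow-up to lose. Nor do they support an expected arm difference in hemorrhagic transformation: Section 3.1 expects no significant increase in intracranial hemorrhage, and a reduction only in recurrent ischemic stroke.

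**Conclusion.** The point holds as a contradiction between Sections 5.7 and 7.5.2 under which follow-up may end at an outcome event, with a misleading completion label and no assurance of the day-180 scan.

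The likely size is modest. As ceilings that assume every event patient leaves, about 3.1 warfarin and 1.3 apixaban patients are affected (about 4% vs 2% of follow-up at mean event day 30), rising to 12 and 5.2 (17% vs 7%) at a risk that counts fatal strokes. Under hemorrhage rates unrelated to recurrence, a true risk ratio of 1.00 is seen as 1.015 to 1.14. Recurrence by arm, event timing and the share of hemorrhages missed are assumptions.

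If recurrence falls as hypothesised, the bias runs against apixaban. It would not manufacture a safety claim for apixaban, but it could hide a safety advantage. It is worth correcting because the loss depends on outcome and would, on the trial's own hypothesis, differ by arm.

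**What to change.** - In Section 5.7, remove recurrent stroke and hemorrhagic transformation from the definition of completion, and remove the qualifier that limits the follow-up duty to patients who stop for other reasons.
- Separate stopping study drug from leaving the study. State that every randomised patient is followed to day 180 for all endpoints, including the already scheduled EOS scan, whatever event occurs, unless the patient dies or withdraws consent.
- Reconcile the follow-up sentence in Section 7.5.2 with this. The rules on suspending the drug need not change.
- In Sections 8.1.3 and 8.1.4, say how a patient without a day-180 scan is coded, and extend the missing-outcome sensitivity analysis to intracranial hemorrhage.

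The cost is protocol wording plus visits and a scan already in the Schedule of Study Procedures. On the ceilings above, that is about 4 patients (3.1 + 1.3) and at most about 17 (12 + 5.2, some of them fatal), plus any with hemorrhagic transformation, for whom the plan gives no expected number.
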